4.3. Justification for Dose

The dosing guidance for starting doses and dose titrations of LY3209590 and insulin degludec are derived based on findings from Phase 2 studies and model-based simulations. These data informed the development of a titration algorithm to safely and efficiently initiate and guide LY3209590 and insulin degludec dose adjustments to achieve the same glycemic goals of FBG between 80 and 120 mg/dL (4.4 and 6.6 mmol/L), while minimizing hypoglycemia risk.

See Section 6.5 for dose modification and titration details.

LY3209590

Initial loading dose

The initial loading dose aims to optimize and accelerate glycemic control by allowing participants to reach a steady-state concentration faster. The use of a single one-time-only loading dose enables participants to achieve concentrations close to steady state within a few

days rather than a period of weeks. This approach minimizes the significant titrations while reaching steady state.

Participants randomly assigned to LY3209590 will receive a single loading dose of 300 U of LY3209590, which equals 3 times the starting weekly dose of 100 U.

This approach is supported by the Phase 2 Study BDCL and PK model-based simulations.

Starting weekly dose

The second dose is the starting weekly dose of 100 U, unless hypoglycemia is observed after the initial loading dose, requiring a dose reduction.

Dose Adjustments

Assessments for dose adjustment will occur from the third dose onwards. Dosing will be individualized based on FBG and hypoglycemia events, and adjustments should occur weekly from Visits 5 to 15 (Weeks 2 to 12) and then every 4 weeks thereafter.

Insulin degludec

Insulin degludec will be titrated to achieve the FBG target using an algorithm that is patterned after the well-established Riddle algorithm but modified to balance efficacy and hypoglycemia risk for the same FBG targets as LY3209590.

Starting dose

The starting dose is 10 U, consistent with the insulin degludec label.

Dose Adjustments

Dosing will be individualized based on FBG and hypoglycemia events, and adjustments should occur weekly from Visits 4 to 15 (Weeks 1 to 12) and then every 4 weeks thereafter.

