6.5.1.1. LY3209590 General Dosing Information by Visit

This table provides general dosing information across visits for all participants randomly assigned to LY3209590.

LY3209590 General Dosing Information		
Visit (Week)	Dose	Additional dosing instruction
Visit 3 (Week 0) initial loading dose	300 U	CAUTION: Do NOT repeat administration of the loading dose.
Visit 4 (Week 1) starting weekly dose	100 U	If a participant experiences hypoglycemia in the previous week, then reduce the starting weekly dose to 60 U, a 40 U reduction based on adjustments for hypoglycemia (see Section 6.5.1.3).
Visits 5-15 (Weeks 2-12)	Doses will be individualized based on FBG and hypoglycemia events	Dose modifications may occur weekly.
After Visit 15	Doses will be individualized based on FBG and hypoglycemia events	Dose modifications may occur every 4 weeks.

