6.5.1.2. LY3209590 Dose Adjustment Based on FBG

This table provides guidance for dose adjustments based on median FBG from the 3 most recently recorded FBG data from the previous week.

If the participant experienced any documented BG ≤ 70 mg/dL (≤ 3.9 mmol/L) in the previous week, the dose should not be increased.

If the median FBG is...		Then...
mg/dL	mmol/L	
<80	<4.4	reduce the LY3209590 dose by 20 U.
80-120	4.4-6.6	do not change the dose.
121-140	6.7-7.7	increase the LY3209590 dose by 20 U.
>140	>7.7	increase the LY3209590 dose by 40 U.

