6.5.2.1. Insulin Degludec General Dosing Information by Visit

This table provides general dosing information across visits for all participants randomized to insulin degludec.

Insulin degludec General Dosing Information		
Visit	Dose	Additional dosing instruction
Visit 3 (Week 0) starting dose	10 U/day	
Visits 4-15 (Weeks 1-12)	Doses will be individualized based on FBG and hypoglycemia events	Dose modifications may occur weekly
After Visit 15 (Week 12)	Doses will be individualized based on FBG and hypoglycemia events	Dose modifications may occur every 4 weeks

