CGM parameters (treatment regimen estimand)	The baseline will be derived from the data collected during CGM session prior to the first dose date of study treatment. Multiple imputation will be used to impute missing observations at baseline.	The CGM session prior to Visit 24 (Week 26) and Visit 31 (Week 52) in EAS1 Multiple imputation approach will be used to impute missing observations at Visit 24 (Week 26) and Visit 31 (Week 52).
CGM parameters (efficacy estimand)	The baseline will be derived from the data collected during CGM session prior to the first dose date of study treatment.	The CGM sessions prior to Visit 7, 15, 24, and 31 (Weeks 4, 12, 26, and 52) in EAS2 for MMRM

Analysis	Baseline Observations	Post-Baseline Observations
Insulin dose during the treatment period	N/A	
All scheduled visits between Visit 3 and Visit 31 in EAS2 for MMRM.
 
The averages of weekly basal insulin doses between visits for individual participants will be used in the analysis. (Section 4.4.2.1)

Fasting glucose by SMBG	
The baseline period is the lead-in period up to the day of first dose of study treatment. Baseline will be derived as the average of all fasting glucose measurements between V2 date and the first dose date.
 
Multiple imputation will be used to impute missing observations at baseline for treatment regimen estimand.
	
All available data after the day of first dose of study treatment up to Week 52 (Visit 31) in EAS2 for MMRM (efficacy estimand).
 
Values at each visit will be derived as average of all fasting glucose measurements from the day post prior visit up to the day of next visit.
 
Data at Week 26 (Visit 24) and Week 52 (Visit 31) in EAS1 for ANCOVA with multiple imputation for missing data (treatment regimen estimand).

Fasting serum glucose	
The baseline is the last non-missing assessment prior to or on the day of the first dose of study treatment.
 
Multiple imputation will be used to impute missing observations at baseline for treatment regimen estimand.
	
All scheduled visits after the day of first dose up to Week 52 (Visit 31) in EAS2 for MMRM (efficacy estimand)
 
Planned measurements at scheduled visits will be included.
 
Data at Week 26 (Visit 24) and Week 52 (Visit 31) in EAS1 for ANCOVA with multiple imputation for missing data (treatment regimen estimand)
 
.

Analysis	Baseline Observations	Post-Baseline Observations

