4.4.2. Supportive secondary Endpoint(s)

4.4.2.1. Other Efficacy Endpoints

The analysis of change from baseline for HbA1c at Week 26, fasting glucose by SMBG at Week 26 and 52, CGM (except for variability) parameters at Week 26 and 52 will be performed for both treatment regimen estimand and efficacy estimand. The analyses for other supportive efficacy endpoints will be based on the EAS2 data.

For treatment regimen estimand, only participants with an observation at baseline or at the endpoint visit will be included in the analysis. The missing baseline will be imputed using multiple imputation under assumption of missing at random. Missing data at the endpoint visit will be imputed using either retrieved dropout or return-to-baseline multiple imputation approach determined by the criterion described for the primary efficacy endpoint in Section 4.3.2. ANCOVA analysis will be conducted similar to that for the primary endpoint. An additional term of baseline HbA1c stratum ($<8.0\%$, $\geq 8.0\%$) will be added into the model for the endpoints other than HbA1c.

For efficacy estimand, participants with baseline and at least one post baseline observation will be included in the analysis. The longitudinal observations of actual and change from baseline in HbA1c to Week 26 will be analyzed using the same MMRM model as for the efficacy estimand described in Section 4.3.2. The analyses of other continuous efficacy measures (fasting glucose, insulin dose and CGM parameters) will use an MMRM model similar to that for the primary endpoint with an additional term of baseline HbA1c stratum ($<8.0\%$, $\geq 8.0\%$). The variance-covariance structure in the MMRM models for fasting glucose from SMBG and insulin dose will be based on compound symmetry.

Longitudinal logistic regression model with baseline value, strata (country, GLP-1 use at randomization, SU use at randomization and baseline HbA1c stratum [$<8.0\%$, $\geq 8.0\%$]), Treatment, Time, and Treatment-by-time interaction as factors will be used for analysis for CGM targets of glycemic control. See Section 4.3.2 for variance-covariance structure selection.

The time point for primary CGM data analysis is CGM session. In addition, the average time in glucose range, hypoglycemia range and hyperglycemia range by week (by visit for treatment period) will be summarized by treatment. Average daily time within each range since last dose

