by CGM Session during treatment period will also be summarized for LY3209590. Missing data patterns will be summarized at daily, weekly (visit) and CGM session levels.

For CGM parameters, data from participants in China using Libre Freestyle H system will be analyzed separately ([Appendix 6](#) [Section 6.6]).

The analysis of study insulin dose will use an MMRM model on the EAS2 data with treatment, strata (country, GLP-1 RA treatment at randomization, SU use at randomization, and baseline HbA1c stratum [$<8.0\%$, $\geq 8.0\%$]), visit and treatment-by-visit interaction as covariates. The average weekly dose during each visit for individual participants will be used in the analysis. In the LY3209590 group, the average dose of each visit (that is, average of weekly doses since last visit) will be used as the average weekly dose. In the insulin degludec group, the average weekly dose will be calculated by the average daily dose multiplying by 7. The analysis will be repeated for average daily dose in U and daily dose in U/kg. The body weight at the visit will be used to calculate the daily dose in U/kg at the same visit.

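### Insulin-dose MMRM: one common variance over Visits 3 to 31 probably makes the Week 52, and likely the Week 26, dose intervals too narrow, by an amount the documents do not fix

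*SAP*

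**What the plan says.** SAP 4.4.2.1 fixes the covariance for two supportive models: "The variance-covariance structure in the MMRM models for fasting glucose from SMBG and insulin dose will be based on compound symmetry". For insulin dose it names no alternative structure, robust variance or sensitivity analysis. The HbA1c model in SAP 4.3.2 instead starts unstructured and works down a list in which compound symmetry with heterogeneous variances is third and compound symmetry without them is sixth and last.

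For the visits in the dose model, the table in SAP 4.1 gives "All scheduled visits between Visit 3 and Visit 31 in EAS2 for MMRM". In the LY3209590 arm, "the average dose of each visit (that is, average of weekly doses since last visit) will be used as the average weekly dose". The model has no baseline-dose covariate. SAP 4.4.2.1 adds: "The analysis will be repeated for average daily dose in U and daily dose in U/kg".

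The protocol sets the early doses. LY3209590 participants receive 300 U and then 100 U, with an instruction after hypoglycemia to "reduce the starting weekly dose to 60 U" (6.5.1.1). Degludec starts at 10 U/day (6.5.2.1). SAP Appendix 14 records a lower start that some Japanese participants could choose. After that, dosing is individual. For degludec, "adjustments should occur weekly from Visits 4 to 15 (Weeks 1 to 12) and then every 4 weeks thereafter" (Protocol 4.3); LY3209590 follows the same pattern from Visit 5. The largest single upward step for LY3209590 is to "increase the LY3209590 dose by 40 U" (6.5.1.2).

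**The concern.** Compound symmetry without qualification uses a single variance for all visits. Here the protocol makes equal variance implausible: the spread of dose within an arm is close to zero at the start and has to grow as titration separates participants. A variance averaged over early and late visits is too small for the late ones, and the late ones are reported.

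Insulin dose at Weeks 26 and 52 is a listed secondary endpoint, and SAP 4.1 has treatment differences shown with 95% CIs and p-values. Those intervals would tend to be too narrow. The same structure carries into the U/day and U/kg repeats and, as far as the text shows, into the GLP-1 RA subgroup model for dose in SAP 4.7.2.1. The Kenward-Roger adjustment, taken over from the primary model, is model-based and does not repair a wrong covariance.

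**Working it through.** The documents give no SD, power or precision for insulin dose, so there is no figure of the plan to reproduce. The check asks how far a common variance can mislead under stated assumptions.

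**1. Formula.** With complete data and a treatment-by-visit mean, the between-arm difference at visit t has true variance proportional to that visit's variance, v(t). Compound symmetry replaces v(t) by the average of v over all visits. So

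model SE / true SE at t = √(mean of v over visits / v(t)),

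and the actual coverage of a nominal 95% interval is 2Φ(1.96 × ratio) − 1. Sample size cancels.

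**2. Visit weeks (Schedule of Activities).** Visits 3–15 fall at Weeks 0 to 12: 13 visits, sum 78. Visits 16–31 fall at Weeks 14, 16, 18, 20, 22, 23, 24, 25, 26, 28, 32, 36, 42, 48, 50 and 52: 16 visits, sum 476. Together there are 29 visits, sum 554, mean 19.1.

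**3. Closed-form results for assumed variance shapes.**

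| Assumed variance | Week 26 ratio (coverage) | Week 52 ratio (coverage) |
|---|---|---|
| None at the first three visits, constant after | √(26/29) = 0.95 (94%) | 0.95 (94%) |
| Linear to Week 12, then flat: (78 + 16 × 12)/29 = 270/29 | √((270/29)/12) = 0.88 (92%) | 0.88 (92%) |
| Linear to Week 52 | √(19.1/26) = 0.86 (91%) | √(19.1/52) = 0.61 (77%) |

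**4. If Visit 3 carries no value.** The first dose is given at Visit 3, so an average since the last visit may leave that visit empty. With 28 values the first two rows become √(26/28) = 0.96 and √((270/28)/12) = 0.90. Little changes.

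**5. Simulated titration.** Doses were generated from the protocol's start doses and step sizes, with assumed individual requirements. Compound symmetry was then fitted by REML to 444 per arm with 15% dropout. The first column is the assumed mean LY3209590 requirement in U/week and its CV.

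| Mean / CV | Week 52 model SE vs empirical SD | Week 52 ratio (coverage) | Week 26 ratio (coverage) |
|---|---|---|---|
| 200 / 0.4 | 4.20 vs 4.69 | 0.90 (92%) | 0.88 (92%) |
| 300 / 0.6 | 6.48 vs 8.35 | 0.78 (87%) | 0.82 (88%) |
| 450 / 0.7 | 7.98 vs 11.51 | 0.69 (82%) | 0.80 (87%) |

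A wider grid (mean 150–450, CV 0.3–0.9) gave 0.81–0.96 at Week 26 and 0.68–0.98 at Week 52. A separately built simulation gave 0.82–0.97 and 0.65–0.99, with or without the hypoglycemia dose rules. The U/kg repeat gave 0.84–0.91 and 0.75–0.90. The most extreme assumption tried, with mean doses near 500 U/week and still climbing at Week 52, gave 0.76 and 0.54.

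**6. What would reverse the direction.** If the dose SD rises linearly to Week 12 and then falls 20% by Week 52, the Week 52 ratio is 0.98; a larger fall would take it to 1 or above. If the SD rises linearly all the way to Week 52, the Week 26 ratio is 0.93, so Week 26 needs most of the spread to arise later still.

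**7. Remedies.** In the simulation, heterogeneous compound symmetry on Visits 5–31 gave 93–97% coverage, and sandwich standard errors gave 93–96%. Dropping Visits 3–4 but keeping a common variance gave ratios of 0.85–0.91 at Week 26 and 0.75–0.90 at Week 52, so that step alone is not a cure.

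**The case against.** The SAP does not say equal variance in so many words. Its list in 4.3.2 qualifies both forms, so the bare term in 4.4.2.1 is not tied to either. This stands as a reason to ask for clarification. The unqualified term ordinarily means one variance, though, and if the heterogeneous form was meant the problem largely goes.

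An unstructured matrix over 29 visits needs 29 × 30/2 = 435 parameters, so a parsimonious choice is defensible. That is true, but heterogeneous compound symmetry needs only 29 + 1 = 30 and is already on the SAP's list.

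All the spreads are assumed, and where individual need varies little the effect nearly vanishes. This stands in full: the figures illustrate the effect and do not bound it.

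Descriptive SDs by visit, which SAP 4.1 requires, would reveal unequal spread. They would show the problem without correcting the interval.

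A reader might also extend the point to fasting glucose by SMBG, which shares the quoted sentence. The argument here rests on protocol-set starting doses. Fasting glucose has no such fixed start, so the documents do not support the extension.

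**Conclusion.** The point holds as a likely understatement of uncertainty. It assumes that compound symmetry carries its usual meaning and that dose spread grows from a near-constant start, as the titration schedule implies. Across the plausible assumptions examined, the SE ratio runs from about 0.98 to about 0.65–0.7 at Week 52 and from about 0.97 to 0.8 at Week 26; extreme assumptions go lower. Week 52 is the firmer of the two.

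Two stronger readings are not supported. One is that the dose intervals are certainly too narrow, or too narrow by a known amount: neither document gives a dose SD at any visit, and a material fall in spread after Week 12 would reverse the direction. The other is that the trial's error control is compromised: SAP 2.1 leaves dose outside the alpha-controlled family, and no primary or key secondary conclusion depends on this model. It is a modest point, worth correcting because correction is cheap.

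**What to change.** In SAP 4.4.2.1, for insulin dose in U/week, U/day and U/kg, and for the GLP-1 RA subgroup dose model in 4.7.2.1:

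- Specify a heterogeneous-variance structure, for example heterogeneous compound symmetry or heterogeneous Toeplitz, fitted to Visits 5–31. Leave out Visits 3–4, where the value is the protocol-set start and the within-arm variance is near zero; keeping them could make visit-specific variances degenerate.
- If that structure does not converge, keep compound symmetry and report empirical (sandwich) standard errors.
- If heterogeneous compound symmetry was already intended, say so.

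This takes a few sentences in the SAP. No protocol amendment is needed, because the protocol leaves the details of this analysis to the SAP. The cost is somewhat wider dose intervals if the spread behaves as expected.

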Participant-reported hypoglycemia	The baseline period is the lead-in period prior to the first dose date of study treatment.	
 Treatment period starts on the first dose date of study treatment and ends 
 At Week 52 (Visit 31) if completed treatment on the last dose date of study treatment + 10 days for LY3209590, +1 day for degludec if discontinued study treatment early Post-treatment period starts from 
 Week 52 (Visit 31) +1 day if completed treatment last dose date of treatment +11 days for LY3209590, +2 days for degludec if discontinued study treatment early and ends on the last date in the study
TEAEs	The baseline period includes the screening/lead-in period up to the first dose of study treatment (The AE Start Relative to Exposure Assessment CRF is used to determine).	Safety analysis period starts after the first dose and ends at the last visit in the study including safety follow-up period.
Safety laboratory tests, vital signs, and body weight	
The baseline will be the last non-missing assessment prior to or on the first dose date of study treatment
 
Planned measurements at scheduled visits will be included.
	
 All scheduled visits after the first dose date up to Visit 802 for MMRM or ANCOVA 
Planned measurements at scheduled visits will be included.

laboratory values elevated or low, vital signs and body weight categorical measures	
Starts from the screening visit and ends prior to or on the day of first dose of study treatment .
 
All available measurements at scheduled and unscheduled visits will be included. The baseline for weight will be the last non-missing value during the baseline period.
	
Starts after the day of first dose of study treatment and ends at the last visit in the study including both treatment period and follow-up period.
 
All available measurements at scheduled and unscheduled visits in the specified analysis period will be included.

Analysis	Baseline Observations	Post-Baseline Observations
Anti-LY3209590 antibody	Refer to PSAP	Refer to PSAP
Patient-reported outcomes	The baseline will be the data collected at Visit 3	
 • All scheduled visits after Visit 3 • Last collection after Visit 3

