Analysis Model	
After the imputation, the observed and imputed data will be analyzed by the ANCOVA model using treatment, strata (country, GLP-1 RA treatment at randomization, and SU use at randomization), and baseline value of the dependent variable as independent variables. The statistical inference will be based on the multiple imputation framework by Rubin (1987).
	
The MMRM model will include treatment, strata (country, GLP-1 RA treatment at randomization, and SU use at randomization), visit and treatment-by-visit interaction as fixed effects, and baseline of the dependent variable as a covariate. The Kenward-Roger approximation will be used to estimate denominator degrees of freedom for the MMRM models. An unstructured covariance structure will be used to model the within-participant errors. If this structure fails to converge, the following covariance structures will be used in order until one converges:
 
 1. Toeplitz with heterogeneity 2. autoregressive with heterogeneity 3. compound symmetry with heterogeneous variances 4. Toeplitz 5. Autoregressive 6. compound symmetry without heterogeneous variances.

Abbreviation: ANCOVA = analysis of covariance; MMRM = mixed model repeated measurement.

The 2-sided 95% CI of the LS mean difference (LY3209590 – insulin degludec) in the HbA1c change from baseline to Week 52 (Visit 31) will be estimated. For both estimands, LY3209590 will be declared noninferior to insulin degludec if the upper limit of the 2-side 95% CI for the LS mean difference in the HbA1c (measured in %) change from baseline is below NIM of +0.4%. In addition, the 95% CI for the LS mean difference will be compared to an alternative NIM of +0.3%.

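### The insulin-dose model in units adjusts for no body weight or other continuous baseline covariate, although pre-dose weight is available; the cost is some precision, not bias

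*SAP*

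**What the plan says.** SAP 4.4.2.1 sets the model out in full: "The analysis of study insulin dose will use an MMRM model on the EAS2 data with treatment, strata". The strata are given as "strata (country, GLP-1 RA treatment at randomization, SU use at randomization, and baseline HbA1c stratum" (below 8.0%, or 8.0% and above), and the remaining terms are visit and treatment-by-visit. The same section says: "The analyses of other continuous efficacy measures (fasting glucose, insulin dose and CGM parameters) will use an MMRM model similar to that for the primary". That refers to the HbA1c model, to which the HbA1c stratum is added. The primary MMRM in SAP 4.3.2 has "baseline of the dependent variable as a covariate". For insulin dose that term does not exist: the table in SAP 4.1 gives its baseline as not applicable.

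Body weight appears once in the dose analysis. The SAP says: "The analysis will be repeated for average daily dose in U and daily dose in U/kg", and "The body weight at the visit will be used to calculate the daily dose in U/kg at the same visit".

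For body weight as an endpoint in its own right, SAP 4.1 does define a pre-dose value: "The baseline will be the last non-missing assessment prior to or on the first dose date of study treatment". The Protocol's schedule (1.3.1) takes weight at Visits 1, 2 and 3.

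On covariance, SAP 4.4.2.1 says: "The variance-covariance structure in the MMRM models for fasting glucose from SMBG and insulin dose will be based on compound symmetry". SAP 4.1 uses all scheduled visits from Visit 3 to Visit 31.

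**The concern.** The baseline value of an endpoint is usually its strongest baseline predictor, so it does most of the work in reducing residual variance. Dose in insulin-naïve participants has no such value, and the obvious candidate to stand in for it is body size. The plan gives reasons to expect weight to matter. The SAP itself repeats the analysis per kilogram. Protocol 5.1 admits a BMI up to 45 kg/m² with no lower limit. Protocol 6.5 starts and titrates both arms in fixed units, not per kilogram, towards a common fasting glucose target. Any difference in requirement that goes with body size should therefore show up in the titrated dose, which is what is compared at Weeks 26 and 52.

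If weight predicts dose within strata, leaving it out keeps that variation in the error term and the confidence intervals are wider than the collected data require. SAP 4.7.2.1 builds the GLP-1 RA subgroup analysis of dose on the same terms, and adds separate models in each subpopulation, so the omission carries into samples about half the size.

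**Working it through.** **The plan's own figure.** Neither document states a power, SD, effect size or weight correlation for insulin dose, so there is no dose figure to reproduce. The only sample-size input used here is the number of completers: 888 × 0.85 = 754.8, which matches the stated 754, or 377 per arm.

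**Formula.** Let r be the partial correlation between baseline weight and dose in units, given treatment and strata. In a single-visit ANCOVA, adding weight multiplies the residual variance by 1 − r². In units of the residual dose SD:

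SE = √(2/377) × √(1 − r²) = 0.0728 × √(1 − r²)

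r is an assumption, shown over a range:

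| r (assumed) | 1 − r² | SE (SD units) | Cut in SE | Equivalent completers, 754/(1 − r²) |
|---|---|---|---|---|
| 0 | 1.00 | 0.0728 | 0% | 754 |
| 0.2 | 0.96 | 0.0714 | 2.0% | 785 |
| 0.3 | 0.91 | 0.0695 | 4.6% | 829 |
| 0.4 | 0.84 | 0.0668 | 8.3% | 898 |
| 0.5 | 0.75 | 0.0631 | 13.4% | 1005 |

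A single-visit regression simulation with 754 participants and three binary strata agrees. At r = 0.3 the SE was 0.0718 with strata and 0.0686 with strata plus weight; at r = 0.5 it was 0.0745 and 0.0641.

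**How the planned covariance structure changes this.** The table applies to one visit. Compound symmetry fits one residual variance across all visits, so the reported SE at Week 52 reflects the average reduction over visits. Early doses are set by the protocol and can depend little on weight, so that average is lower than the reduction at the endpoint visit.

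To illustrate, take the 29 scheduled visits from Week 0 to Week 52. Assume that the dose SD rises linearly to Week 26 and is then flat (relative SD s, with Σs² = 13.98), and that r reaches 0.5.

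- r follows the same shape as the SD: Σs⁴ = 11.65, so the variance factor is 1 − 0.25 × 11.65/13.98 = 0.792. Its square root is 0.890, a cut of 11.0%.
- r rises linearly until Week 52: Σs²(week/52)² = 5.74, so the factor is 1 − 0.25 × 5.74/13.98 = 0.897. Its square root is 0.947, a cut of 5.3%.

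Both are below the single-visit 13.4%. The SD and correlation profiles are assumptions; only the visit schedule comes from the documents.

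**Does the U/kg repeat fill the gap?** It divides the outcome by weight at the same visit. That changes the quantity compared. The divisor is also measured after randomization, and change in weight is itself a listed treatment comparison. The model in units stays exactly as precise as before.

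**The case against.** The strongest reply is that this is an efficiency preference and not an error. Randomization is central, 1:1 and stratified, so omitting a prognostic covariate does not bias the comparison. Insulin dose is a supportive secondary endpoint with no multiplicity adjustment, margin, power statement or success rule, and no stated conclusion depends on the width of its interval. The size of the loss rests on a correlation that the documents do not give. All of this stands, and it limits the point without removing it.

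Four stronger readings are tempting, and the documents do not support them.

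- *That the dose model has no individual baseline predictor.* GLP-1 RA use, SU use and baseline HbA1c stratum are participant-level pre-treatment characteristics, and all are in the model. What is missing is weight, or any continuous baseline covariate.
- *That a chance weight imbalance is a separate, uncorrected harm.* With 444 per arm, such imbalance lies within about 1.96 × √(2/444) = 0.13 SD in 95% of randomizations, and the unadjusted interval already allows for it. It is the precision point again.
- *That the U/kg repeat fails because weight is not taken at telehealth visits.* Weeks 26 and 52 are not telehealth visits, and change in weight at both weeks is a listed endpoint.
- *That the loss is large.* Nothing in the documents supports a high partial correlation once the strata are in the model. At r of 0.2 or less the gain is 2% or less.

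**Conclusion.** The point holds as a small, nearly free gain in precision. The dose-in-units MMRM has no body weight and no continuous baseline covariate, nothing stands in for the missing baseline dose, and a suitable pre-treatment measurement is already collected and defined. The U/kg repeat does not supply the adjustment.

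The size is uncertain: a cut in the SE of 0% to 13.4% for an assumed partial correlation of 0 to 0.5 on the single-visit approximation, and probably less in the model-based SE under pooled compound symmetry. The treatment comparison remains valid as planned. This is a desirable refinement, not a defect that threatens any conclusion.

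**What to change.** In SAP 4.4.2.1, add baseline body weight (the last non-missing value on or before the first dose date, as SAP 4.1 already defines it) and its interaction with visit to the insulin-dose MMRM for weekly and daily dose in units. Carry the same terms into the dose model in SAP 4.7.2.1. The interaction lets the weight slope be near zero while doses are set by the protocol and grow as titration takes effect. Leave the U/kg analysis unchanged.

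The cost is one SAP edit and some model degrees of freedom: at most one slope for each of the 29 visits, which is minor with about 754 completers. No new data are needed and the endpoint does not change. If weight turns out not to predict dose, almost nothing is lost.
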